2. STUDY OBJECTIVES

2.1. Primary Objective

Evaluate the disease progression using the ALSFRS-R functional scale and the FVC of subjects affected by ALS treated with PE using Albutein 5%.

2.2. Secondary Objectives

Evaluate the effects of PE using Albutein 5% on:

- Cognitive dysfunction
- BMAA chronic toxicity
- Neurofilament levels
- Systemic inflammatory response

2.3. Safety Objectives

Evaluate the effects of PE using Albutein 5% on:

- Safety and tolerability of the procedure, including AEs, clinical laboratory testing,

physical examination, and vitals signs.

3. INVESTIGATIONAL PLAN

3.1. Study design/Development phase

Development Phase	Phase IIa
Study Design	Pilot, single-center, prospective, open-label and single arm study
Randomization procedures and treatment assignment	Not applicable for an open-label study with a single treatment
Type of control	Not applicable
Masking Techniques	Not applicable
Follow-up period	Subjects will be followed up for 6 months after the final PE treatment

4. SELECTION OF STUDY POPULATION

Subjects of both genders who are older than 18 years of age and younger than 70, who have an ALS diagnosis, and who give their consent to participate after having been duly provided signed informed consent by the investigator may be included in this study.

Both untreated subjects and subjects on a stable dose of Riluzole for at least 28 days may be enrolled.

4.1. Inclusion and Exclusion Criteria

4.1.1. Inclusion Criteria

A subject must meet all the following inclusion criteria to be eligible for participation in this study:

1. Signed informed consent.
2. Subjects over 18 years of age and less than 70 years old.
3. Subjects with a possible, probable-lab supported, probable, or definite diagnosis of ALS, according to the revised El Escorial criteria.
4. Subjects having experienced their first ALS symptom within 18 months prior to recruitment/consent.
5. FVC > 70%.
6. Subjects must be medically suitable for study participation and willing to comply with all planned aspects of the protocol, including blood sampling, at the time of inclusion in the study.

4.1.2. Exclusion Criteria

A subject meeting any of the following exclusion criteria is NOT eligible for participation in this study:

1. Subjects with pre-existing clinically significant lung disease not attributable to ALS.
2. Subjects diagnosed with other neurodegenerative diseases or diseases associated with other motor neuron dysfunction.
3. Participation in another investigational product study within one month prior to screening.
4. Females who are pregnant, breastfeeding, or, if of child-bearing potential, unwilling to practice a highly effective method of contraception (oral, injectable or implanted hormonal methods of contraception, placement of an intrauterine device or intrauterine system, condom or occlusive cap with spermicidal foam/gel/film/cream/suppository, male sterilization, or true abstinence) throughout the study.
5. Difficult or problematic peripheral vein access and inability to implant a central catheter which would make continuous PE not feasible as per the visit protocol.
6. Contraindication to undergo PE or subject has abnormal coagulation parameters at the discretion of the outpatient apheresis unit team, including but not limited to:
 - a) Thrombocytopenia (platelets <100,000/ μ L)
 - b) Fibrinogen <1.5 g/L
 - c) International normalized ratio (INR) >1.5
 - d) Beta-blocker treatment and bradycardia <50 beats/min
 - e) Treatment with angiotensin-converting enzyme inhibitors which may increase the risk of allergic reactions
7. History of anaphylaxis or severe systemic response to any plasma-derived albumin preparation, component of Albutein 5%, or other blood product(s).
8. Subjects unable to interrupt treatment with acetylsalicylic acid, other oral antiplatelet, or anticoagulant.
9. Renal dysfunction by elevated creatinine concentration >2 mg/dL.
10. Presence of heart disease that contraindicates PE treatment, including ischemic cardiopathy and congestive heart failure.
11. Presence of prior behavioral disorders requiring pharmacological intervention with less than 3 months of stable treatment.
12. Mentally challenged subject who cannot give independent informed consent.
13. Any condition that would complicate compliance with the study protocol (i.e., illness with the expectation of less than one year survival, abuse of drugs or alcohol, etc.).

4.2. Diagnosis of ALS

Due to the variability of the early clinical symptoms of the disease and the lack of an early diagnostic biomarker, diagnosing ALS may be difficult. Frequently the symptoms are not recognized until motor function has been lost and the average delay in diagnosis is approximately one year.^(3,36) Several biomarker candidates for ALS have been identified (proteins, neurophysiological and neuroimaging parameters), but none of them have been

sufficiently validated for diagnostic or prognostic purposes.(9,36) The current ALS diagnosis is fundamentally clinical and is based on the revised El Escorial criteria.(37-41) The ability to study a homogeneous population in an early stage of the disease may be difficult due to delay in diagnosis and differences in clinical presentation of the disease.

According to the revised El Escorial criteria, the ALS diagnosis consists of:

The presence of:

(A1) clinical, neurophysiological, and neuropathological signs of lower motor neuron involvement; (A2) clinical signs of upper motor neuron involvement; and (A3) symptoms and signs, confirmed by the clinical history and examination, must be progressive with subsequent involvement of different anatomical regions.

together with the absence of:

(B1) electrophysiological or pathological signs of other diseases that could explain upper motor neuron and/or lower motor neuron involvement, and (B2) neuroimaging studies with lesions that could explain the clinical signs and electrophysiological findings.

Therefore several categories of ALS diagnosis can be described:

- **Clinically definite ALS:** clinical evidence alone of upper and lower motor neuron signs in three regions.
- **Clinically probable ALS:** clinical evidence alone of upper and lower motor neuron signs in at least two regions with some upper motor neuron signs rostral to (above) the lower motor neuron signs.
- **Clinically probable–laboratory-supported ALS:** clinical signs of upper and lower motor neuron dysfunction are in only one region, or upper motor neuron signs alone in one region with lower motor neuron signs defined by electromyography criteria in at least two limbs, together with proper application of neuroimaging and clinical laboratory protocols to exclude other causes.
- **Possible ALS:** clinical signs of upper and lower motor neuron dysfunction in only one region, or upper motor neuron signs alone in two or more regions; or lower motor neuron signs rostral to upper motor neuron signs and the diagnosis of clinically probable-laboratory-supported ALS cannot be proven.

4.3. Number of subjects

The number of subjects planned to be included in this study is 10 subjects completing the planned treatment. There has been no formal calculation for the sample size since this is a pilot study.

The sample size is considered adequate for the evaluation of the objectives of the study. In addition, there is a rising consensus in the ALS field that active control group comparisons should be avoided in early trials.(42)

Lastly, the current EMA guidance document, *Guideline on clinical investigation of medicinal products for the treatment of amyotrophic lateral sclerosis (ALS)* (EMA/CHMP/4015/2013) states that the average functional decline is about 1 point per month in untreated subjects on the ALSFRS-R Functional Scale (primary variable of this study).(34) Thus, it may be assumed that 10 treated subjects followed during 1 year of the clinical trial would be sufficient to evaluate a change of disease progression rate. In the event that a move towards

stabilization is observed, the subsequent confirmatory studies will require a formal calculation for the sample size.

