PROTOCOL SYNOPSIS

Study Title :	Pilot study to evaluate the efficacy and safety of plasma exchange with Albutein® 5% in patients with amyotrophic lateral sclerosis
Name of the Sponsor:	GRIFOLS BIOLOGICALS Inc. [name]
Name of Investigational Product:	Albutein® 5%
Protocol ID Number:	GBI1501
Name of active ingredient:	Human Serum Albumin
Indication:	Amyotrophic Lateral Sclerosis (ALS)
Study Centers:	Single-center at Dartmouth-Hitchcock Medical Center (DHMC), Lebanon, NH.
Study Design:	Pilot, phase IIa, prospective, open-label and single-arm study
Objectives:	
Primary Efficacy Objective: Evaluate disease progression using a Amyotrophic Lateral Sclerosis Functional Rating Scale – Revised (ALSFRS-R) and the forced vital capacity (FVC) of subjects affected by ALS treated with plasma exchange (PE) with Albutein 5%.
 
Secondary Objectives: Evaluate the effects of PE using Albutein 5% on:
 
 – Cognitive dysfunction – Beta-methylamino-L-alanine (BMAA) chronic toxicity – Neurofilament levels – Systemic inflammatory response 
Safety Objectives: Evaluate the effects of PE using Albutein 5% on:
 
 – Safety and tolerability of the procedure, including adverse events (AEs), clinical laboratory testing, physical examination, and vitals signs
Methodology:	This pilot study plans to enroll 10 subjects who have a definite, possible, or probable diagnosis of ALS, according to the revised El Escorial criteria. Enrolled subjects will be treated with PE with Albutein 5% as a replacement solution during an Intensive Treatment Phase of 2 PEs per week over 3 weeks followed by weekly PE for 21 weeks (Maintenance Treatment Phase). A 6-month follow up will begin after the last PE.

Duration of the treatment:	Six (6) months (24 weeks) of PE treatment with Albutein 5% and 6 months follow-up after last PE.

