Since ALS is a rapidly progressive disease, we plan to combine a first Intensive Treatment Phase followed by a Maintenance Treatment Phase in accordance with the progressive nature of the disease with the objective of obtaining disease stabilization or improvement.

A current European Medicines Agency (EMA) guidance document states that the average functional decline is about 1 point per month on the ALSFRS-R in untreated subjects.(34) However, disease progression has been found to be highly variable and does not always follow a linear descent.(35,36) Therefore, the treatment will be considered efficacious when a subject's rate of decline is lower than the expected decline or disease progression assessed by ALSFRS-R.

For all the reasons mentioned above, we propose a pilot study with the objective of treating 10 ALS-diagnosed subjects, with PE using Albutein 5%.

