4.5. Estimated duration of recruitment period

The recruitment period is estimated to take approximately 6 months in order to include 10 subjects.

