11.5. Determination of sample size

The sample size has not been calculated formally because this is a pilot study. The decision

to recruit 10 subjects was reached to obtain the information necessary to meet the objectives of the study and to verify proof of concept of the use of PE with Albutein 5% in ALS patients.

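### The planned 10 is defined as treatment completers in protocol 4.3 and SAP 3.3 but as intake everywhere else, with no dropout allowance or stated replacement rule

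*Protocol*

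**What the plan says.** Protocol section 4.3, repeated in SAP section 3.3, sets the size by completion: "The number of subjects planned to be included in this study is 10 subjects completing the planned treatment". Both sections report no formal calculation, call the sample adequate, and argue that 10 subjects followed for one year are enough to evaluate a change in progression rate.

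Four other places in the protocol attach the same number to intake:

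- Synopsis, Methodology: "This pilot study plans to enroll 10 subjects".
- Section 1.2: "we propose a pilot study with the objective of treating 10 ALS-diagnosed subjects". The SAP introduction also speaks of treating 10.
- Section 4.5: recruitment is expected to take "approximately 6 months in order to include 10 subjects".
- Section 11.5: the decision "to recruit 10 subjects was reached to obtain the information necessary".

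Section 4.4 lists nine reasons for withdrawal and bars a withdrawn subject from coming back. Section 5.2 adds withdrawal for refusing a central line when one is indicated. Section 6.2.3 treats 27 exchanges as a maximum and allows sessions to be omitted. No section gives a dropout rate, an over-enrolment margin or a rule on replacing non-completers.

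**The concern.** Ten completers and ten enrolled are the same number only if nobody is lost. The treatment runs to as many as 27 plasma exchanges over 24 weeks, in a disease for which section 1.1 reports 60% mortality within three years, so some attrition is foreseeable.

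The label matters because section 4.3 rests its adequacy statement on this figure, and following 10 subjects for a year asks for more than 10 finishing 24 weeks of treatment. SAP 6.3.4 tests change from baseline at each visit and compares ALSFRS-R change with a decline of one point per month. SAP 6.6 imputes nothing, and a single missing item voids the ALSFRS-R total. Results at Weeks 25 and 48 therefore use only the subjects still observed, and the Per-Protocol set contains only treatment completers. If 10 is really intake, those results will probably have fewer than 10 behind them unless attrition is very low, and nothing in the plan tells the reader to expect that.

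**Working it through.** **The plan's own figure.** The 10 cannot be reproduced. No effect size, SD, power or dropout rate is given, and both documents say no formal calculation was made. The check is therefore whether the two uses of 10 can both hold.

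**What is counted in each place.**

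| Place | What the 10 counts |
|---|---|
| Protocol 4.3, SAP 3.3 | treatment completers |
| Synopsis | enrolled |
| Protocol 1.2, SAP 1 | treated |
| Protocol 4.5 | included |
| Protocol 11.5 | recruited |

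**Chance that all 10 complete.** Assume exactly 10 enter, none is replaced, and each independently fails to complete with probability d. The value of d is an assumption, shown over a range. Then P = (1 − d)^10 and the expected number of completers is 10(1 − d). The last two columns give the intake needed for an expected 10 completers, 10/(1 − d) rounded up, and the smallest intake with at least an 80% binomial chance of 10 or more completers.

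| d | P(all 10 complete) | Expected completers | Intake for expected 10 | Intake for 80% chance |
|---|---|---|---|---|
| 2% | 0.98^10 = 0.82 | 9.8 | 11 | 10 |
| 5% | 0.95^10 = 0.60 | 9.5 | 11 | 11 |
| 10% | 0.90^10 = 0.35 | 9.0 | 12 | 12 |
| 20% | 0.80^10 = 0.11 | 8.0 | 13 | 14 |
| 30% | 0.70^10 = 0.03 | 7.0 | 15 | 16 |

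**Break-even.** Setting (1 − d)^10 = 0.5 gives d = 1 − 0.5^0.1 = 0.067. Above 6.7% a shortfall is more likely than not; below it, all 10 would more likely than not complete.

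**The one attrition-related rate in the documents.** Section 1.1 gives 60% dead within three years among ALS patients generally. At a constant hazard this is −ln(0.40)/3 = 0.305 per year.

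- 24 weeks: survival exp(−0.305 × 24/52.18) = 0.869, so 13.1% mortality; 0.869^10 = 0.25.
- 48 weeks: survival exp(−0.305 × 48/52.18) = 0.755, so 24.5% mortality; 0.755^10 = 0.06.

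This is an illustration, not a forecast. It probably overstates deaths here, because entry requires FVC above 70% and first symptoms within 18 months, and excludes illness with expected survival under one year. On the other side, it leaves out every withdrawal other than death. It also shows why Weeks 25 and 48 need separate expected numbers.

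**Precision.** The half-width of a 95% interval for a mean is t(0.975, n − 1)/√n in SD units: 0.715 at n = 10, 0.836 at n = 8 and 0.925 at n = 7. Relative to n = 10 the interval is 17% wider at n = 8 (0.836/0.715 = 1.17) and 29% wider at n = 7 (0.925/0.715 = 1.29).

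**The case against.** A reader might infer that the trial caps intake at 10 and forbids replacement. The documents do not say that. Section 4.4 bars only the same withdrawn subject from returning and is silent on new subjects. Section 4.3 can be read as recruiting until 10 complete, and section 10.5 foresees amendments that raise the number treated. This objection stands: what is missing is a stated rule, and the arithmetic above is conditional on no replacement.

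A reader might also infer that the trial will probably fall short of 10 completers. That needs dropout above 6.7%. Such a rate is plausible for this regimen and disease, but a list of permitted withdrawal reasons is not a rate, and at 5% or less all 10 would more likely than not complete.

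The harm is limited too. The protocol describes a descriptive, single-arm pilot with no power target or promised precision. The main efficacy analysis uses the Evaluable population, which requires one exchange, a baseline and a later measurement, not completion. Withdrawn subjects are to be asked to a final visit. Because sessions may be omitted, someone who receives fewer than 27 exchanges is not clearly a non-completer.

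None of this reconciles the two labels. If recruitment continues until 10 complete, the four intake statements are wrong and intake has no stated ceiling. The Evaluable headcount can remain at 10 while the number observed at late visits falls. And the option of omitting sessions shows that completion itself is undefined.

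**Conclusion.** The point holds as an inconsistency in a figure the plan relies on. One number carries two meanings, and they agree only with zero attrition or with a replacement rule that is not written down. That much needs no assumption.

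The size of any shortfall does need assumptions: intake of exactly 10, no replacement, independent losses and a dropout rate the documents do not supply. Across 2% to 30% dropout, the chance of 10 completers runs from 0.82 to 0.03 and the expected number from 9.8 to 7.0. The consequence is a smaller Per-Protocol set, fewer subjects at late visits and somewhat wider intervals there. The documents do not support going further, to a claim that the pilot is invalid or that a power or precision target is missed, because none was set.

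**What to change.** Use one figure, with one meaning, throughout both documents.

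- **If 10 is intake:** restate protocol 4.3 and SAP 3.3 to say that 10 subjects will be enrolled and treated. Give the expected number with data at Week 25 and at Week 48 separately, with the dropout assumed for each, and base the adequacy statement on those numbers. This costs wording only and needs no extra enrolment; the adequacy statement becomes slightly less favourable.
- **If 10 completers is the intent:** correct the intake figures in the synopsis and sections 1.2, 4.5 and 11.5 (and the SAP introduction), and state that non-completers are replaced. This may mean treating more than 10. Treating 12 is a 20% increase (12/10 − 1), above the 15% at which section 10.5 calls for the authorities and the IRB to be informed; treating 11 is a 10% increase.

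In either case, define treatment completion for analysis purposes, since sessions may be omitted and the Per-Protocol set depends on it.

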4.4. Withdrawal criteria and stopping rules

Subjects may withdraw or be withdrawn from the study for any of the following reasons:

1. At subjects' own request.
2. If, in the Investigator's opinion, continuation in the study would be detrimental to the subjects' well-being.
3. At the specific request of the sponsor.
4. Development of clotting or bleeding disorders due to a decrease in platelets and/or coagulation factors as a result of PE.
5. Non-compliance with inclusion or exclusion criteria.
6. Subjects with an occurrence of a concomitant disease or any medical condition which, either because of its severity or duration or necessary change in treatment, contravenes the condition of the study or puts the subject at unnecessary risk or harm.
7. Subjects with an occurrence of an AE which in the opinion of the Investigator and/or subject requires termination of treatment.
8. Subjects who are noncompliant with the protocol.
9. Subjects who develop an infection with hepatitis A virus (HAV), hepatitis B virus (HBV), hepatitis C virus (HCV), or human Immunodeficiency virus (HIV 1 & 2) during the study. Though subjects will not be routinely tested for these pathogens during the trial, they will be under a physician's supervision throughout the study. A subject should be withdrawn if, in the opinion of his/her physician, he/she develops any of these viral infections.

The cause for the withdrawal will be documented. A final visit should be set up to obtain blood samples from the subject and for the subject to complete the final visit testings and assessments. Once the withdrawal is completed, subjects may not be readmitted to the study.

Under the following circumstances the study team will recommend to halt the trial temporarily (until modifications to the protocol are completed) or wholly (abandon all study activities):

- Temporarily halt the trial if more than 30% of subjects undergoing plasma exchange procedures have an SAE as defined as related to the Investigational Product (remember that if causal relationship of the SAE is labeled as "definite", "probable", "possible" or "doubtful/unlikely", the event will be defined as a suspected adverse drug reaction) and not attributable to the therapeutic procedure or technique of application, as judged by the principal investigator and Sponsor, requiring that both parties agree.
- Completely stop the trial if more than 50% of subjects undergoing plasma exchange procedures have an SAE as defined as related to the Investigational Product (remember that if causal relationship of the SAE is labeled as "definite", "probable", "possible" or "doubtful/unlikely", the event will be defined as a suspected adverse drug reaction) and not attributable to the therapeutic procedure or technique of application, as judged by the principal investigator and Sponsor, requiring that both parties agree.

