5.2. Plasma Exchange (PE)

This study will evaluate the effects of PE with Albutein 5% in treating ALS.

PE involves a non-selective removal of plasma proteins among which include various coagulation related proteins and factors. Therefore, a transient coagulopathy is an anticipated and expected side effect related to the procedure but this has not been reported to increase the overall patient risk profile.

These transient changes are normally reverted in 24 hours following the procedure. During the intensive phase of the study the treatment regimen is of 2 PE procedures per week spaced out by a minimum of 48h apart to ensure the safety of each subject.

PE will be preferably carried out by a peripheral venous access. It is recommended that each PE be performed at a rate of 40 to 100 mL/min with a continuous flow blood cell separator.

Peripheral access must be assessed at the baseline visit (V0), which consists of a subjective assessment of peripheral veins by the nursing staff of the DHMC.

If during the course of treatment phase there is an inability to achieve extraction flows greater than 45 mL/min on 2 consecutive PE sessions, the subject will be offered the possibility of installing a central venous access line. Subjects who do not consent to the central venous access lines when indicated will be withdrawn from the study.

Volume to be exchanged: 100 to 110% of the plasma volume based on gender, weight, and the hematocrit of the subject.

PE will be carried out with a Cobe Spectra or Optia blood cell separator, using a citrate solution (ACD-A) as anticoagulant in a ratio of 1:10 and continuous infusion of calcium gluconate 1 g per hour of procedure.

The approximate duration of the process will be 1.5 to 3 hours. This also includes preparation time and subsequent monitoring after the PE. The subject will remain in the DHMC facilities, being monitored by the nursing staff during the entire process per standard operating procedures of the Outpatient Apheresis Unit.

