7.1.2. Adverse Event Monitoring

Subjects must be carefully monitored for AEs. This monitoring includes clinical and laboratory tests and physical signs. AEs should be assessed in terms of their seriousness, severity, and causal relationship to the investigational product.

The investigator is responsible for the detection and documentation of events that comply with the criterion and definition of an AE or a serious adverse event (SAE), in accordance with that set forth in this protocol. AEs and SAEs will be documented from the time the subject signs the informed consent before the first PE and until the subject returns for the last study visit, whether the subject has completed the study or has stopped prematurely for any reason.

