7.1.4. Reporting of Serious Adverse Events

7.1.4.1 Reporting Serious Adverse Event

Any SAE (see [section 7.1.3.6](#)) that occurs after **signing the study ICF through Week 48 (i.e., end of study)** must be expeditiously reported whether or not considered attributable to the study drug or study procedure. Each SAE must be fully recorded in the subjects CRF and SAE form.

In addition, any SAE that occurs greater than 28 days after the last dose of investigational product should be reported if the Investigator feels that the event is related to the use of investigational product.

SAEs will be reported using the designated SAE form. When the Investigator becomes aware of an SAE, she/he must submit by email/fax a completed, signed, and dated SAE Report Form **within 24 hours** to the Sponsor.

Each SAE must be followed up until resolution or stabilization. After the initial report, all relevant information for SAE follow up, and for the outcome, must also be supplied to the Sponsor in a timely manner (within 3 days from its identification or within 24 hours for relevant new information) by means of the SAE Report Form. In addition, the Sponsor (or Contract Research Organization [CRO]) may request additional information and/or reports.

All SAE Report Forms must be reported to:

Grifols Global Pharmacovigilance
Email: [REDACTED]
FAX (back.-up only): [REDACTED]
and
Send to [REDACTED]

When required, and according to local law and regulations, SAEs must be reported to the IRB/EC and regulatory authorities.

There may be situations in which an SAE has occurred and the investigator has minimal information to include in the initial report. In such cases it is important for the investigator to make an evaluation of the relationship for each event prior to the submission of the SAE form because this evaluation is used to determine the requirements of the reports issued to regulatory authorities. The investigator may change his opinion for the causal relationship once he/she has additional information and rectifies the SAE reports if necessary.

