16.2.1.1 Study termination
16.2.1.2 Treatment termination
16.2.1.3 Subject discontinuation
16.2.1.4 Visit dates

16.2.2. Protocol deviations.

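### The protocol does not separate stopping plasma exchange from leaving the study, so follow-up of early stoppers is unreconciled and can shrink to one undated visit

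*Protocol*

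**What the plan says.** **Status after stopping.** Protocol 4.4 opens: "Subjects may withdraw or be withdrawn from the study for any of the following reasons". Item 7 is "Subjects with an occurrence of an AE which in the opinion of the Investigator and/or subject requires termination of treatment", and item 4 is a clotting or bleeding disorder resulting from PE. Both are events of treatment, and the status they lead to is study withdrawal. Section 5.2 goes further for vascular access: "Subjects who do not consent to the central venous access lines when indicated will be withdrawn from the study". Of what follows, 4.4 says "A final visit should be set up to obtain blood samples from the subject and for the subject to complete the final visit testings", without an interval from the last PE or from the decision. It adds: "Once the withdrawal is completed, subjects may not be readmitted to the study".

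**End of collection.** Section 7.1.2 documents AEs and SAEs "until the subject returns for the last study visit, whether the subject has completed the study or has stopped prematurely for any reason", and 7.1.3.7 stops at the last day of participation. Section 7.1.4.1 sets SAE reporting from "signing the study ICF through Week 48 (i.e., end of study". Section 3.1 promises 6 months of follow-up after the final PE and does not limit this to completers. Sections 6.2.7 to 6.2.9 tie V4 to PE#27 (Week 25), V5 to Week 36 and V6 to Week 48.

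**SAP.** Section 8.3 has a listing "16.2.1.2 Treatment termination" beside one for study termination, but neither document defines the two. The AE summary in SAP 6.3.8 and Table 14.3.2.2 count only discontinuation from the study. SAP 6.6 does not impute missing values. SAP 6.3.4 tests the change in ALSFRS-R against a fixed decline of 1 point per month.

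**The concern.** Neither document describes a subject who has permanently stopped PE and remains on the visit schedule. A site following 4.4, 5.2 and 7.1.2 as written can close such a subject out with one visit at any time. The subjects affected include those who stop because of a reaction, a coagulation problem or failed access. They are the ones for whom later safety information matters most.

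For safety, the loss would be of scheduled questioning for new events, later safety laboratory tests, and serology taken long enough after exposure to be informative. For efficacy, the later ALSFRS-R and FVC tables would rest mainly on subjects who continued PE. In a single-arm study of about 10 subjects compared with a fixed reference rate, there is no control arm in which the same selection could be seen.

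**Working it through.** The plan states no power, dropout or event figure, so there is nothing to reproduce. The check has three steps.

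**1. When does follow-up end?** Inputs are 3.1 (6 months, which is 24 weeks on the protocol's own schedule, Week 48 − Week 24), 7.1.2 and 7.1.4.1.

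| Source | Completer (last PE Week 24) | Last PE Week 8 |
|---|---|---|
| 3.1, 6 months after final PE | 24 + 24 = Week 48 | 8 + 24 = Week 32 |
| 7.1.2, subject's last visit | V6, Week 48 | final visit, undated |
| 7.1.4.1, SAE reporting | Week 48 | Week 48 |

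The three agree for a completer and diverge for an early stopper.

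**2. What is lost if the subject is withdrawn?** Post-baseline ALSFRS-R and FVC are due at Weeks 4, 12, 25, 36 and 48 (6.1.1).

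- Stop at Week 8: Weeks 12, 25, 36 and 48 remain, so 4 of 5 visits are replaced by one undated visit. Scheduled AE questioning lost is at most 48 − 8 = 40 weeks, less any delay to the final visit.
- Stop after the Week 12 visit and before Week 25: Weeks 25, 36 and 48 remain, so 3 of 5.
- Serology (HIV, HCV, HBsAg) is scheduled only at V0 and V6 (6.2.1). A completer is tested 48 − 24 = 24 weeks after the last PE. For an early stopper no minimum interval is stated. The visit could fall inside the 72-hour window used for the session AE/AR variables (6.1.3).

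**3. What could this do to the efficacy tables?** The documents give no SD and no dropout rate, so these are illustrations under stated assumptions.

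- *Precision at Week 48.* Half-width of the 95% CI = t(0.975, n−1) × SD/√n, with SD of change assumed to be 2 to 6 points. For n = 10 it is 1.4 to 4.3 points; for n = 7 it is 1.9 to 5.6 points.
- *Placing the undated visit.* If a Week 8 exit visit were tabulated as V6, then at 1 point per month and 30.4375/7 = 4.348 weeks per month (the month length in SAP 6.3.10) the expected change is −8/4.348 = −1.84 instead of −48/4.348 = −11.04. The subject looks 9.20 points better than expected, and one such subject in 10 moves the mean by 0.92. Counting 4 weeks per month, as the protocol's 24 weeks for 6 months implies, the figures are 12 − 2 = 10 points and 1.0. The SAP has no rule that excludes this.
- *Selective loss, worst case.* Assume normally distributed slopes, a true mean of exactly −1 point per month, and loss of the 1, 2 or 3 fastest decliners of 10. In 200,000 simulated sets, the chance that the one-sample t-test wrongly favours treatment rises from 2.5% to about 9%, 19% and 31%. These rates barely change for slope SDs from 0.3 to 0.8. Loss of the slowest decliners would bias the result the other way. Nothing in the documents says which subjects will stop.

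**The case against.** The other side has good points, and several of them stand.

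- **Withdrawal is mostly permissive.** Section 4.4 says subjects may be withdrawn. Section 6.2.3 lets single PEs be omitted for laboratory, clinical or AE reasons without withdrawal, and 3.1 can be read as keeping everyone for 6 months. A reader might infer that anyone who stops PE must leave the study. The documents say so only for refusal of an indicated central line.
- **Safety follow-up is not wholly lost.** Under 7.1.3.9, known events are followed to resolution as far as possible. Section 7.1.4.1 keeps SAEs reportable to Week 48, and late SAEs if judged related. A reader might infer that a subject who stops at Week 4 loses 44 of 48 weeks of all safety collection, or is guaranteed no follow-up at all. Neither inference holds. The weeks apply only to scheduled visits and active questioning for new events, and the gap after the last PE is unspecified rather than set at zero.
- **The exit visit has content.** Read with 6.2.9 it includes safety laboratory tests, serology, ALSFRS-R and FVC. Its timing is what is missing.
- **Disease decline is not a withdrawal reason.** It could enter only through the subject's request, the investigator's opinion or a concomitant condition (items 1, 2 and 6). The worst-case simulation is therefore a bound and does not describe what 4.4 produces.
- **Early stoppers stay in the analysis sets.** They remain in the Safety Population, and in the Evaluable Population if they meet its measurement requirement.

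None of this supplies a status for a subject who is off PE and still in the study, a date for the exit visit, or agreement between 3.1, 7.1.2 and 7.1.4.1.

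**Conclusion.** The point holds in this form: the documents do not distinguish stopping PE from leaving the study, and their follow-up provisions agree for completers but conflict for early stoppers. If 4.4, 5.2 and 7.1.2 are followed as written, a withdrawn subject has 3 or 4 of the 5 post-baseline co-primary visits, scheduled questioning for new AEs, and late laboratory tests and serology replaced by one undated visit. Each such subject is about 10% of the sample if 10 are enrolled, as in the Synopsis; 4.3 instead counts 10 completing treatment.

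With no imputation, later visits would over-represent subjects who continued PE. It would go too far to say that the withdrawal rule biases the result whatever analysis is used. Direction and size depend on who stops and why, and no dropout rate is given. The passages should be reconciled, but this is not a fatal flaw in a pilot study.

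**What to change.** 1. In Protocol 4.4 and 5.2, define discontinuing PE and withdrawing from study follow-up as two separate statuses. Leave the reasons for stopping PE as they are.
2. Ask subjects who discontinue PE to attend the remaining visits by study week for ALSFRS-R, FVC and AE/SAE review, and for the Week 48 safety laboratory tests and serology, unless they withdraw consent to follow-up. Anchor V4 to Week 25 for those who never reach PE#27.
3. For subjects who leave altogether, date the final visit so that AE collection covers at least the 72 hours after the last PE.
4. Reconcile 3.1, 4.4, 5.2, 6.2.7, 7.1.2, 7.1.3.7 and 7.1.4.1 on when AE and SAE collection ends.
5. In the SAP, define treatment termination and study termination, tabulate an early final visit by its actual week and not as V6, and list on-PE or off-PE status at each assessment.

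The cost is protocol, SAP and consent wording; the visits already exist for every subject. The downside is that some subjects will attend visits without treatment, and some will decline.
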